To date there has only been one published trial of gut-directed hypnotherapy for functional dyspepsia, but with promising results⁸. Calvert and colleagues found that 73% of patients in the hypnotherapy group had significant improvement in dyspeptic symptoms at long-term follow-up, compared to 34% of patients receiving supportive therapy plus a placebo pill and 43% of patients receiving medical treatment. Additionally, patients in the hypnotherapy group had dramatic reductions in medication use and physician consultations at follow up.

The goal of the current study is to develop and conduct a pilot test of effectiveness of a self-administered gut-directed hypnotherapy intervention for treatment of FD, with the aim of assessing its potential as an inexpensive, easy-to-use and efficacious treatment for the disorder.

II. Background and Significance/Preliminary Studies

Background and Significance

Both patients and providers are frustrated by the limited treatment options for FD. This is a chronic condition and many patients continue to seek medical care for poorly managed symptoms, including multiple physician office visits and investigative procedures. More effective treatment options are needed to reduce this health care burden. Behavioral treatments (e.g., gut-directed hypnotherapy) are highly effective for other functional gastrointestinal disorders and have shown promise for FD.⁶ However, additional research is needed to establish behavioral treatment as an efficacious and realistic approach for this condition.

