There have been a few trials of very diverse forms of psychotherapy in FD with varying degree of reported success⁸⁻¹⁸; however, no treatment has had adequate testing and all of them involve a course of many visits to a highly specialized mental health professional which is expensive and not available in most places. To date, one of the most successful and best designed trials of this kind has been Calvert et al.'s randomized controlled study of hypnotherapy for FD⁸. This trial found significant improvements in FD symptoms and significant reductions in health-care utilization following a course of hypnotherapy with superior results compared to the two control groups and there was full maintenance of the treatment effect beyond one year follow-up. These therapeutic effects demonstrate impressive potential for hypnosis as a therapy option in FD. However, it is notable that the intervention tested by Calvert et al. consisted of a 12-session course of treatment with a specialized GI hypnotherapist, which means that generalizability of this approach is very limited due to significant cost barriers and limited availability of therapy expertise. However, other work in GI hypnosis, including two studies of co-investigator [name], has demonstrated that hypnosis treatment that is self-administered by patients via audio recordings without any therapist involvement can be highly efficacious in improving GI symptoms^{19,20}. That form of delivery could make hypnotherapy a much more widely available treatment option if proven effective, as it could be delivered in a very inexpensive and easily disseminated form. Our present study therefore aims to replicate the findings by Calvert et al. demonstrating that hypnosis treatment (HYP) can lead to clinically significant improvements in dyspeptic symptoms, while testing it in an audio-recorded easy-to-use self-administered format.

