A published pilot study of hypnotherapy for IBS delivered entirely through audio recordings by co-investigator [name] and his colleagues serves as a model for the hypnosis treatment in this FD trial¹⁹. That study found that IBS patients who completed a seven-session self-administered audio home hypnosis treatment course were twice as likely (53% vs 26%) to have a reduction in their gastrointestinal symptoms by half or more at 6 months compared to matched control patients of the same age and sex and equal symptom severity who only received standard medical care. We will script the audio-recorded hypnosis protocol in the present trial to be similar in structure and therapy approach, as IBS and functional dyspepsia are both functional GI disorders and have many similarities and a high degree of overlap (the intervention tested in the prior hypnosis trial by Calvert et al., that showed high success in FD treatment, also utilized modified IBS hypnosis treatment for that purpose).

III. Study Aims

The purpose of this pilot study is to develop and test a hypnotherapy (HYP) treatment program for functional dyspepsia (FD) that can be self-administered using on-line audio recordings. We hypothesize that patients will be receptive to the self-administered treatment design and willing to participate and complete the 12-week treatment program.

Furthermore, we expect that patients will experience a significant reduction in FD symptoms following the intervention. Our specific aims include:

Aim 1: Feasibility and Acceptability of Treatment

The study will assess whether patients with FD will be willing to participate in the on-line treatment program and the majority of patients enrolled in the study will complete the 12 week program, utilize the materials sufficiently, and report average to above average satisfaction with treatment.

Aim 2: Treatment Effectiveness

The primary endpoint for Aim 2 is significant reduction in pre- to post- treatment FD symptom scores. Secondary endpoints include significant improvements in pre- to post-treatment score on psychological indices (e.g., anxiety) and disease-specific quality of life.

IV. Administrative Organization

All administrative activities related to the study will take place within the Division of Gastroenterology and Nutrition at Loyola University Medical Center (LUMC).

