Administrative offices for the division are located in the Fahey Building on the LUMC campus where office furniture, file cabinets, and use of essential equipment (e.g., copier, fax, phone, computer) will be provided.

V. Study Design

a. Experimental design of the study:

This is a non-randomized observational study designed to provide preliminary data on the feasibility and effectiveness of a self-administered HYP treatment for FD.

b. Study population general description

Eligible patients will be referred by Gastroenterologists within the Digestive Health Program at Loyola University Medical Center and will have received a diagnosis of functional dyspepsia. Additionally, any patients with functional dyspepsia referred by outside providers to [name] GI Behavioral Medicine Service at LUMC will be made aware of the study.

c. Sample size determination and power analyses

We will enroll 23 adults with FD from the Loyola University Medical Center outpatient gastroenterology practices, with the aim of assessing feasibility and acceptability of HYP treatment using on-line audio recordings. Sample size was determined for aim 1 of the study. Allowing for up to 20% drop-out and having at least 16 patients complete the study through the end of treatment (where the primary endpoint will be measured) will provide sufficient participant feedback on the web interface as well as the pilot data needed to power a future randomized controlled trial.

d. Study outcomes/endpoints

The primary endpoint for this study will be FD symptom scores. Secondary endpoints will be disease-specific quality of life, psychological indices, and patient satisfaction.

VI. Study Procedures

a. Subject selection procedures:

We will enroll 23 adults with FD.

Inclusion criteria

- (1) Diagnosis of functional dyspepsia by a gastroenterologist
- (2) Meeting ROME IV diagnostic criteria for functional dyspepsia
- (3) At least 18 yrs of age (no upper age limit)
- (4) Able to give informed consent
- (5) English speaking
- (6) Have daily personal access to the Internet via laptop or desktop computer, tablet or a smartphone.

Exclusion criteria

- (1) Concomitant organic gastrointestinal disease
- (2) Diagnosed or presenting with serious mental illness (e.g., eating disorder, schizophrenia, psychosis, obsessive-compulsive disorder, post-traumatic stress disorder, or a dissociative disorder)

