4. What happens with screen failures (including any data gathered during screening)? Data will not be collected on patients that are screened as ineligible for the study. However, these patients will be provided with recommendations for alternative treatment options by their gastroenterologist (medications, diet changes), alternative psychological treatments within the Loyola GI behavioral medicine program, or a referral to an outside provider depending on patients' needs.

- b. Randomization procedures (if applicable): N/A
- c. Study Intervention

Patients will be given access to a password protected website containing HYP treatment materials. They will be instructed by the study coordinator to log on to the website within 1 week to complete baseline assessment questionnaires and watch an instructional video. This video will be pre-recorded by [name] (study PI). The content of the video will include educational information about the patient's diagnosis, provide rationale for hypnotherapy treatment, set expectations for treatment, and dispel myths about hypnotherapy. The video will also provide instructions on implementing the treatment protocol, including guidance on selecting a time and place to practice hypnotherapy and recommendations for weekly practice with audio recordings (5x per week). See Appendix B for a full script of this introductory video (video will be filmed after we receive IRB approval).

We have developed a 7- session, hypnosis protocol for functional dyspepsia that is similar to an evidence-based protocol for irritable bowel syndrome developed by co-investigator [name], which has been found to be efficacious in 7 published studies²⁴. This protocol was jointly scripted by Drs. [name] and [name], and is based on the successful scripted therapy approach for IBS, with appropriate adaptations. See Appendix C for the full scripted protocol of the 7 hypnotherapy sessions as well as the shorter practice session that will be audio recorded. This will be the full content of the audio recordings, subject to final minor edits and polishing, prior to recording which will be scheduled after we receive IRB approval.

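### Aim 2 lets a significant pre- to post-treatment drop in one uncontrolled group stand as treatment effectiveness, which this design cannot show

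*Combined protocol and SAP*

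**What the plan says.** Section III, under the Aim 2 heading Treatment Effectiveness, sets the criterion: "The primary endpoint for Aim 2 is significant reduction in pre- to post- treatment FD symptom scores".

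Section V.a describes the design: "This is a non-randomized observational study designed to provide preliminary data on the feasibility and effectiveness of a self-administered HYP treatment for FD". Section VI.b confirms that nobody is allocated: "Randomization procedures (if applicable): N/A". No comparison group or run-in is described, and VI.d has a single pre-treatment assessment, at week 0.

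Section VIII analyses Aim 2 with linear mixed models adjusted for baseline and says that they estimate treatment effects at each follow-up.

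Section II says that the study aims to replicate the randomized hypnotherapy trial in functional dyspepsia (FD), "demonstrating that hypnosis treatment (HYP) can lead to clinically significant improvements in dyspeptic symptoms". The Abstract reports that trial as a contrast: 73% improved on hypnotherapy, "compared to 34% of patients receiving supportive therapy plus a placebo pill and 43% of patients receiving medical treatment". Preliminary Studies reports the audio-recorded IBS study as a contrast too: 53% against 26% of matched standard-care controls had symptoms reduced by at least half at 6 months.

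On size, V.c says "Sample size was determined for aim 1 of the study". It adds that the expected completers will give feedback on the website "as well as the pilot data needed to power a future randomized controlled trial". It does not say which quantities from the pilot the RCT would use.

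**The concern.** With one group, the only contrast the model can supply is time. The mean change from baseline to week 12 is the sum of any effect of hypnosis, the natural course of a fluctuating condition, regression to the mean, and placebo response. The data cannot separate these. A significance test of the change asks only whether the sum is zero.

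The criterion in Section III nevertheless attaches the word effectiveness to a significant result, Section VIII attaches treatment effects to the estimate, and Section II attaches replication to a finding that was a difference between randomized arms. No passage mentions natural course, placebo response or regression to the mean as a limit on interpretation.

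At stake is the conclusion that the trial may draw. Following its own criterion, it could report effectiveness when hypnosis contributes nothing. V.c also leaves open whether the pre-post change might later serve as the RCT's effect size.

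**Working it through.** **1. The plan's own figures.** The only power statements, in Section VIII, belong to Aim 1. Both reproduce by exact binomial calculation:

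- Retention: P(X ≥ 16 | n = 23, p = 0.80) = 0.9285, against 92.8% stated.
- Satisfaction: P(X ≥ 8 | n = 21, p = 0.50) = 0.9054, against 90.5% stated.

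No effect size, SD, significance level or power is given for Aim 2, so there is no Aim 2 figure to reproduce.

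**2. Do the documents themselves show improvement without hypnosis?** Yes, in direction.

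| Source in the protocol | Patients | Outcome | Hypnosis | Control |
|---|---|---|---|---|
| Abstract | FD | significant improvement, long-term follow-up | 73% | 34% (supportive therapy plus placebo) |
| Abstract | FD | same | 73% | 43% (medical treatment) |
| Preliminary Studies | IBS | symptoms at least halved, 6 months | 53% | 26% (standard care) |

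None of these is a 12-week change in the symptom score used here. They show that controls improve, not how much this group would.

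**3. How often would the Aim 2 criterion be met if hypnosis adds nothing?** This is an illustration.

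- Completers: V.c plans "Allowing for up to 20% drop-out and having at least 16 patients complete the study through the end of treatment". With 20% drop-out, 23 × 0.80 = 18.4, so n = 18. The stated minimum (16) and full retention (23) give the range.
- Test (assumed): paired t-test, two-sided 0.05.
- Non-specific change d (assumed): 0.3, 0.5 or 0.8 SD of the change score. The documents give no value.
- Formula: P(T > t(0.975, n−1)), where T is noncentral t with n−1 degrees of freedom and noncentrality d√n.
- For n = 18: critical value 2.110; noncentrality 0.3 × 4.243 = 1.273, 0.5 × 4.243 = 2.121 and 0.8 × 4.243 = 3.394.

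| Completers | d = 0.3 | d = 0.5 | d = 0.8 |
|---|---|---|---|
| 16 | 20.2% | 46.5% | 84.8% |
| 18 | 22.4% | 51.6% | 89.2% |
| 23 | 28.0% | 63.0% | 95.6% |

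If the true mean change were zero, a significant reduction would occur in 2.5% of studies.

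**4. Which pilot quantities can inform an RCT?** One treated group can estimate the SD, the baseline to week-12 correlation, retention and missing-data rates. It cannot estimate a between-arm difference. V.c speaks only of pilot data and does not separate the two.

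**The case against.** The strongest reply is that the limitation is declared in substance. The protocol calls itself a pilot giving preliminary data, sizes the study for Aim 1, names an RCT as the next step, and ties its only numerical decision rules to Aim 1. That stands: a single-arm pilot is a legitimate choice, and the point does not ask for a control arm. It does not remove the stated Aim 2 criterion or the wording built on it.

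Three further replies have force.

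- Expectation, the introductory video and the coordinator contacts are part of the programme, so whether they count as non-specific depends on a comparator not yet chosen. Natural course and regression to the mean are not part of the programme under any comparator.
- Regression to the mean is plausible but of unknown size. Recruitment also uses social media and student listservs, and there is no numerical symptom-score threshold for entry.
- The illustration uses a completers' paired test, whereas Section VIII plans a mixed model, and its percentages follow entirely from the assumed d.

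A reader might also infer two stronger things.

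- **That the future RCT will be undersized.** Net response is (73 − 34)/73 = 0.534, (73 − 43)/73 = 0.411 and (53 − 26)/53 = 0.509 of gross response, and 1/ratio² gives 3.5, 5.9 and 3.9 times as many patients. But no passage says that the pre-post change will be the RCT's effect size, and responder proportions need not scale to mean change. The risk is conditional: nothing in V.c rules that use out.
- **That 34%, 43% and 26% can be applied to the 23 patients here, or set beside the results as a benchmark.** Population, outcome definition, time point and care received all differ, so the documents do not support that.

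**Conclusion.** The concern holds as one of criterion and wording. Aim 2 can be met, and effectiveness claimed, without any contribution from hypnosis. How often cannot be known from the documents: about 22%, 52% or 89% of studies with 18 completers if non-specific change is 0.3, 0.5 or 0.8 SD, all assumed values. The conclusion itself needs none of these numbers. It follows from having one group, no comparator and a test of change over time. For the same reason, a significant drop here would not replicate the controlled FD result.

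The choice of a single-arm pilot is not at fault, and the documents do not establish that the later RCT would be too small. The matter is worth correcting because it determines what the trial may conclude, and correcting it needs no new data.

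**What to change.** 1. **Sections III and VIII.** Restate Aim 2 as estimation of the within-group change in FD symptom scores from baseline to week 12, reported with a 95% CI. Replace the terms effectiveness and treatment effects. Add a sentence that a significant drop will not be reported as effectiveness or as replication of the controlled trial, because the change also includes natural course, regression to the mean and placebo response. Align the replication wording in Section II.
2. **Section V.c.** State that the future RCT will take from this pilot the SD, the baseline to week-12 correlation, and the retention and missing-data rates. State that the between-arm effect will come from controlled data or a minimal important difference, not from the pre-post change.

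No table against the cited control rates and no additional responder endpoint is needed.

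Cost: protocol wording only, with no change to data collection or sample size. The downside is a more modest claim for Aim 2.

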In a separate study management web page, study staff will be able to log in to see which main hypnosis sessions each patient has completed and whether they are significantly overdue for completing the next session, and also whether they have completed the study questionnaire at the expected time points, and the frequency of practice of the shorter exercises for each individual. This information will alert the study staff to contact patients who are not keeping up with study tasks with reminders.

d. Study Assessments and Activities

Study Assessments:

At baseline (week 0), week 6 (mid-treatment), week 12 (post-treatment), and at 12 weeks following end of treatment (i.e., 3 month follow up) participants will be asked to complete a set of questionnaires listed below. See Appendix D for a complete list of survey items and questionnaires. Study assessments will be administered electronically through the password-protected online platform via highly secure Qualtrics Research Suite Software, and all questionnaire data will be collected in a fully de-identified manner that neither obtains nor stores online any information that can reveal the personal identify of participants. Participants will be assigned a unique subject code that will be associated with his/her questionnaire data.

Patients will be paid for completing each of the assessments: They will receive Amazon gift certificates in the amount of \$25 each time, except the amount will be \$50 at the end-of-treatment point (as this is the most important assessment time point). Thus, patients will receive a total compensation of \$125 for completing all 4 assessments in the study.

Additionally, participants will be invited to participate in a phone interview to provide qualitative feedback about their experience with the intervention and using the web interface. This will be a semi-structured

interview with the research coordinator to assess patient experience and satisfaction. The interview will take place within one month following the final hypnotherapy session.

Patients will complete the following questionnaires:

- **Demographics** and psychosocial history (administered at week 0 only): basic demographic data (e.g., age, gender, education) as well as disease related information (symptom severity, medication use).

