- **The Rome IV Dyspepsia Module** will be administered at baseline to confirm diagnosis of functional dyspepsia. This self-report questionnaire is used to diagnosis functional GI disorders based on Rome IV criteria.²
- **The Patient Assessment of Upper Gastrointestinal Symptom Severity Index (PAGI-SYM)** will be administered to assess symptom severity. The PAGI-SYM measures 20 dyspeptic symptoms on a 6-point Likert scale, 0 (no complaints) – 5 (severe complaints), subdivided into six subscales: heartburn/regurgitation, nausea/vomiting, postprandial fullness/early satiety, bloating, upper abdominal pain, and lower abdominal pain. The measure has demonstrated good reliability and validity for measuring symptom severity in patients with functional dyspepsia.²⁵
- **The Short Form Napean Dyspepsia Index (NDI-SF)** is a 10-item disease specific quality of life questionnaire developed for clinical trials in functional dyspepsia. The NDI has been established to have excellent psychometric properties²⁶ and responsiveness to treatment change has been confirmed²⁷ and the 10-item short form is recommended for use in clinical trials.²⁸
- **Visceral Anxiety (VSI):** The VSI is a 15-item questionnaire that will be used to assess gastrointestinal specific anxiety²⁹. This measure assesses fears of GI symptoms and is a predictor of symptom severity in patients with functional GI disorders. The VSI uses a 6 point likert scale response format with total scores ranging from 0 to 75; higher scores indicate more severe symptom-related anxiety.
- **The Brief Symptom Inventory (BSI)** will be used to assess depression, anxiety, and somatization.³⁰ The BSI is an 18-item questionnaire using a 5-point likert scale with scores ranging from 0 to 68; higher scores indicate higher levels of distress.
- **Thought Impact Scale- Short Form (TIS-SF).** This 17-item questionnaire is a short-form version of the Thought Impact Scale, a newly validated measure designed to predict clinical response to hypnosis treatment. The TIS-SF will be administered at baseline only to assess whether the traits that it measures (i.e., subconscious

connectedness) correlates with the degree of FD symptom improvement in the study.³¹

- **Adherence to Hypnosis Practice:** Use of hypnosis sessions will be recorded automatically by the audio player page on the treatment web page, to track frequency of home practice of hypnotherapy by the HYP intervention participants.

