- We will take steps to reduce the risk of discomfort associated with answering questions on assessment measures related to psychological functioning by allowing participants to leave blank any questions that may make them uncomfortable. The participant will be reminded that s/he has the option of stopping treatment and can refuse to answer any questions s/he is asked that s/he finds distressing. However, the study team shall determine if the extent of refusal may warrant removal of the participant from the research study to ensure complete and accurate data collection.

b. What procedures will be used to monitor subject safety?

- Participants will be given contact information for study personnel and encouraged to reach out if they experience an increase in psychological distress related to the treatment. Participants will be told that they are welcome to withdraw from the study at any time.
- We plan to use an electronic platform for this study to deliver the hypnotherapy sessions as well as to conduct all patient evaluations online. It is same technology as [name] has used successfully for online data collection in multiple NIH-funded RCT clinical trials. All study questionnaires will be administered electronically in the password-protected online portal via highly secure Qualtrics Research Suite software, and all questionnaire data will moreover be collected in a fully de-identified manner that neither obtains nor stores online any information that can reveal the personal identity of participants. This is accomplished by associating patient responses only with their randomly assigned study ID numbers.
- The online hypnotherapy program is considered an investigational device under the Food and Drug Administration (FDA) regulations and is categorized as a nonsignificant risk device.
- Patient names will be keyed into unique subject code and the keyed file will be kept separate from the data file to ensure patient confidentiality. Data downloads will be stored in a secure study folder in HIPAA-compliant LUMC file server space, with study folder access restricted to IRB-approved study personnel. Any non-electronic study data will be stored in locked filing cabinets, accessible only by IRB-approved study personnel. Data will be stored for 7 years after study completion per IRB policy.

c. Who (list names) will identify, document, and report adverse events?

[name], study PI

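### Removing participants for unanswered questions cannot complete the data and forfeits the later assessments they might have given

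*Combined protocol and SAP*

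**What the plan says.** Section VII.a aims to limit discomfort from "answering questions on assessment measures related to psychological functioning" by "allowing participants to leave blank any questions that may make them uncomfortable". It adds that participants may refuse any question they find distressing. The same bullet then has the study team "determine if the extent of refusal may warrant removal of the participant from the research study to ensure complete and accurate data collection". It sets no threshold and does not provide for continued assessment after removal. No other section limits the clause.

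Section VI.d schedules questionnaires as follows: "At baseline (week 0), week 6 (mid-treatment), week 12 (post-treatment), and at 12 weeks following end of treatment". Four scales are repeated:

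- Symptoms: "The PAGI-SYM measures 20 dyspeptic symptoms on a 6-point Likert scale".
- Quality of life: the NDI-SF "is a 10-item disease specific quality of life questionnaire developed for clinical trials in functional dyspepsia".
- Psychological: "The VSI is a 15-item questionnaire that will be used to assess gastrointestinal specific anxiety", and "The BSI is an 18-item questionnaire using a 5-point likert scale".

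Treatment satisfaction is asked once, at week 12. The Rome IV module is given at baseline to confirm the diagnosis, and meeting Rome IV criteria is an inclusion criterion (section VI.a).

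The Analysis Plan (section VIII) calls retention acceptable if at least 16 of 23 are retained. It counts satisfaction over everyone who started treatment, dropouts included. For Aim 2 it uses mixed models, which it justifies by their behaviour under missing at random.

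**The concern.** The clause works against its own stated purpose. A blank item stays blank when the participant is removed; what changes is that nothing further is collected. The discomfort that section VII.a describes concerns the psychological measures, whereas the primary endpoint in section V.d is the FD symptom score. A participant who declines the psychological items may be willing to report symptoms and quality of life, and removal gives those scores up.

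Two aims are touched. For Aim 2, the mixed model could have used the forfeited symptom and quality-of-life scores, because it does not need complete data from every participant. For Aim 1, someone removed before treatment ends cannot be among the 16 retained, so a staff decision can lower a result meant to show whether patients will complete the programme. Someone removed after starting treatment but before week 12 also stays in the satisfaction denominator and can no longer report being satisfied.

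**Working it through.** **1. What removal costs in assessments.** Inputs are the item counts and visit schedule in section VI.d.

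- Symptom and quality of life: 20 + 10 = 30 items per visit.
- Psychological: 15 + 18 = 33 items per visit.
- Total: 30 + 33 = 63 items per visit.

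Take one assumed participant who skips all 33 psychological items and answers the other 30 every time.

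| Removed after | Visits left | Items missing with removal | Items missing without | Extra loss |
|---|---|---|---|---|
| Baseline | 3 | 3 × 63 = 189 | 3 × 33 = 99 | 90 |
| Week 6 | 2 | 2 × 63 = 126 | 2 × 33 = 66 | 60 |
| Week 12 | 1 | 63 | 33 | 30 |

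The extra loss is entirely symptom and quality-of-life items. The models analyse scale scores, and on that footing removal after baseline costs three PAGI-SYM and three NDI-SF scores, plus the week-12 satisfaction answer. These figures are an upper bound for this pattern of refusal. A participant who would answer nothing later loses nothing more.

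**2. The plan's own retention figure.** Inputs from section VIII, Aim 1: n = 23, null 50%, alternative 80%, reject at 16 or more, one-sided 0.05. With X binomial:

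- Power: P(X ≥ 16 | 23, 0.8) = 0.9285, which agrees with the stated 92.8%.
- Type I error: P(X ≥ 16 | 23, 0.5) = 0.0466. A cut-off of 15 would give 0.1050, so 16 is the smallest valid cut-off.
- Expected completers: 0.8 × 23 = 18.4, a margin of 18.4 − 16 = 2.4 people.

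**3. Retention if k participants are removed before treatment ends.** The documents give no k, so these are scenarios only. Each removal counts as not retained. At k = 0 the figure stays 92.8%.

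| Assumption | Formula | k = 1 | k = 2 |
|---|---|---|---|
| The rest complete at 80% | P(X ≥ 16 \| 23 − k, 0.8) | 86.7% | 76.9% |
| Those removed would have completed at 50%, overall 80% | P(X ≥ 16 \| 23 − k, p), p = (18.4 − 0.5k)/(23 − k) = 0.8136, 0.8286 | 90.1% | 86.3% |
| Those removed would all have completed | P(X ≥ 16 + k \| 23, 0.8) | 84.0% | 69.5% |

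The first row is the plain illustration. The other two show how far it depends on who is removed. Under the null the first scenario gives P(X ≥ 16 | 22, 0.5) = 0.0262 and P(X ≥ 16 | 21, 0.5) = 0.0133, so the type I error is not inflated.

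**The case against.** **The harm is hypothetical.** The wording is discretionary, no removal rate is given, and none may occur. This stands in full. It is why the probabilities are illustrations and the point is minor.

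**Some blanks do bear on a participant's place in the study.** Someone who leaves the baseline Rome IV module blank has not had the diagnosis confirmed by the stated instrument. This stands, and the fix is limited accordingly. A participant with no baseline symptom score would add little or nothing to a model that adjusts for baseline. That limits their use in that model, but it is no reason to end follow-up for other scales, retention and satisfaction.

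**Refusal may extend to symptom items.** Participants may refuse any distressing question, so the split between 33 and 30 items is one pattern among many. This stands as a limit on the item counts. It does not help the clause, since removal fills no blank under any pattern.

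**The purpose also includes accuracy.** The trigger is refusal, though, and a blank is not an inaccurate answer.

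A reader might also infer more than the documents support:

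- *That the retention decision is undefined for staff removals.* The fixed count of 16 of 23 settles it: a person removed before treatment ends has not completed. Only the label and the reported proportion are open.
- *That the clause invalidates the missing-at-random basis of Aim 2.* A link between refusal and distress is plausible, but removal would follow from observed refusal. Neither the size nor the direction of any added bias can be shown.
- *That data already given are discarded.* Nothing says so.

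**Conclusion.** The point holds as a minor one. For participants whose eligibility is confirmed, the removal clause cannot serve completeness and can only lose later symptom, quality-of-life and satisfaction data that they may have been willing to give. It also lets a staff decision reduce the number who can count towards the retention criterion.

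Its size in this trial cannot be estimated from the documents: it is nil if nobody is removed. The retention margin is only 2.4 expected completers, so even one or two removals would be noticeable. The conclusion rests on one reading, that removal from the study ends assessment. That is its plain meaning, and no continued follow-up is provided for. No stated sample size, power or significance level is wrong because of this point.

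**What to change.** Amend section VII.a so that, once eligibility is confirmed (including the baseline Rome IV module), refusing questionnaire items is not a ground for removal. Such participants stay in follow-up and are analysed with all the data they give.

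In section VIII, Aim 1, state that all 23 enrolled remain in the retention denominator. Report any staff-initiated removal as not retained, separately from participant dropout, with its reason and timing.

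Discontinuation for safety is a separate provision and is not affected.

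The cost is a wording amendment and slightly more item-level and scale-level missing data to handle. The sample size, cut-off and stated power do not change.
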